2 LIST OF ABBREVIATIONS

Abbreviation	Expansion
ACR	American College of Rheumatology
AE	Adverse event
CARLOS	Cartilage Loss Score
CDAI	Clinical Disease Activity Index
CI	Confidence interval
CMH	Cochran-Mantel-Haenszel
CMO	Chief Medical Officer
CRF	Case report form
CSR	Clinical study report
DAS	Disease Activity Score
DMARD	Disease-modifying antirheumatic drug
DMC	Data monitoring committee
EDC	Electronic data capture
EGA	Evaluator's global assessment
eGFR	Estimated glomerular filtration rate
EQ-5D-5L	EuroQol 5 domains 5 levels
EULAR	European League Against Rheumatism
H_0	Null hypothesis
H_1	Alternate hypothesis
HAQ-DI	Health Assessment Questionnaire Disability Index
hsCRP	High-sensitivity C-reactive protein
IL	Interleukin
IRB	Institutional Review Board
IRT	Interactive response technology
ITT	Intent to treat
JAKi	Janus kinase inhibitors
LDA	Low disease activity
LOCF	Last observation carried forward

Abbreviation	Expansion
MAR	Missing at random
MCID	Minimal clinically important difference
MedDRA	Medical Dictionary for Regulatory Activities
MMP3	Matrix metalloproteinase 3
MMRM	Mixed-effect Model Repeated Measure
MRI	Magnetic resonance imaging
NRI	Non-responder imputation
NRS	Numerical rating scale
OC	Observed case
PCS	Physical component summary
PD	Protocol deviation
PF	Physical functioning
PMA	Premarket Approval
PT	Preferred term
PTE	Per-treatment evaluable
QC	Quality check
RA	Rheumatoid arthritis
RAMRIS	Rheumatoid Arthritis MRI Scoring System
RF	Rheumatoid factor
SAA	Serum amyloid A
SADE	Serious adverse device effect
SAE	Serious adverse event
SAP	Statistical analysis plan
SAS	Statistical Analysis Software
SD	Standard deviation
SF	Social functioning
SF-36	Short Form Survey with 36 items
SGA	Subject's global assessment
SJC28	Swollen joint count for 28 different joints
SOC	System organ class

Abbreviation	Expansion
SOP	Standard operating procedure
TEAE	Treatment emergent adverse event
TJC28	Tender joint count for 28 different joints
UADE	Unanticipated adverse device effect
USADE	Unanticipated serious adverse device effect
WHO	World Health Organization

3 INTRODUCTION

This document outlines the statistical analysis plan (SAP) for the RESET-RA study conducted by SetPoint Medical under protocol SPM-020 entitled “Vagus Nerve Stimulation Using the SetPoint System for Moderate to Severe Rheumatoid Arthritis: The RESET-RA Study.” The SAP specifies the data listings, tabular summaries, and analyses to be performed for the primary, secondary and exploratory endpoints and safety evaluation using the randomized, controlled, double-blind data through Week 12 to support an application for Premarket Approval (PMA).

The data listings, tabular summaries, and analyses to be performed for the exploratory endpoints and long-term safety evaluation using the open-label follow-up data through Week 264 are detailed in a separate SAP (CLP-008). The PMA application will include supporting data on long-term safety for all subjects for whom long-term data are available at the time of application.

3.1 Study Objective

The overall objective of this study is to evaluate the safety and efficacy of the SetPoint System for the treatment of adult patients with active, moderate to severe RA who have had an inadequate response or intolerance to biologic or targeted synthetic DMARDs.

3.2 Study Design

This is an operationally seamless, 2-stage, randomized, sham-controlled, double-blind, multicenter pivotal study enrolling at least 240 and up to 250 randomized subjects at up to 45 study centers across the U.S. Enrollment will be conducted in 2 consecutive stages:

- Stage 1 with 60 randomized subjects at up to 25 study centers; and
- Stage 2 with approximately 190 randomized subjects at up to 45 study centers, including those from Stage 1.

There will be a pause in enrollment after enrollment in Stage 1 is completed. This pause in enrollment is intended to allow completion of Week 12 assessments by 60 enrolled and randomized subjects and an interim analysis (see Section 4.2). The primary analysis will occur after the last enrolled and randomized subject in Stage 2 completes Week 12 assessments, which is defined as the last subject’s Week 12 visit (see Section 4.3).

After completing primary endpoint assessments at Week 12, there will be a one-way crossover of control subjects to active stimulation and a 252-week open-label follow-up with all subjects receiving active stimulation to evaluate long-term safety. Blinding will be maintained until the last enrolled and randomized subject in Stage 2 completes Week 12 assessments, and the study dataset for the primary analysis is locked.

3.3 Study Visits and Assessments

On the same day that written consent is obtained, each subject will undergo physical examination, RA disease activity assessments and review of prior and current RA medications to confirm their initial eligibility and baseline values for the primary and key secondary efficacy endpoints. The

remaining screening assessments, including blood work and pre-surgical clearance, will be completed prior to Implant Procedure, which shall be performed within 30 days from informed consent. Post-Surgical Clearance will be performed between 14 and 21 days from Implant Procedure. Day 0 assessments, randomization and initial device titration will be performed after completing Post-Surgical Clearance and within 14-21 days from Implant Procedure. There will be 3 additional device titration visits (Titration 1, 2, 3 at Week 1, 2 and 3, respectively), 3 follow-up RA assessment visits (Week 4, 8, 12 primary efficacy endpoint and a one-way crossover) as detailed in Schedule of Assessments (see **Appendix A**).

During open-label, long-term follow-up there will be 3 device titration visits (Titration 4, 5, 6 at Week 13, 14, 15, respectively), and 21 follow-up RA assessment visits every 12 weeks from Week 24 through Week 264 (end of study) as detailed in CLP-001.

3.4 Sample Size and Power

The sample size is calculated based on an estimated 60% response rate at Week 12 in the treatment group and 30% response rate at Week 12 in the control group. A sample size of 250 randomized subjects, 125 in each group, offers 96% power to detect a difference of 30% at the one-sided alpha of 0.025. If the true response rates are 50% in the treatment and 30% in the control group, the sample size of 250 subjects has 77% power to detect a difference of 20% at the one-sided alpha of 0.025. The table below provides additional power calculations for 250 subjects using estimated response rates of 20 to 40% in control and 35-70% in treatment (**Table 1**). The table also shows power if enrollment ends at 240 subjects. The decrease in power is <1% for all scenarios and most often <0.5%.

Table 1: Power Calculation Based on Estimated ACR Response Rate

Control (%)	Treatment (%)	Difference (%)	Power N = 250	Power N=240
20	50	30	0.967	0.966
20	45	25	0.917	0.916
20	40	20	0.812	0.807
20	35	15	0.609	0.601
30	60	30	0.959	0.959
30	55	25	0.900	0.898
30	50	20	0.773	0.770
30	45	15	0.555	0.549
40	70	30	0.959	0.958
40	65	25	0.897	0.893
40	60	20	0.762	0.750

All p-values are one-sided based on the chi-square test stratified incomplete response to JAKi and include futility stopping. Power based upon 1,000,000 simulations per scenario.

The smallest statistically significant difference that can be detected in the sample of 250 randomized subjects ranges from 11.2% to 12.8% for control rates of 20% to 40%, respectively.

4 TYPE OF PLANNED ANALYSIS

4.1 DMC Analysis

An independent Data Monitoring Committee (DMC) consisting of external, independent rheumatology, surgery and biostatistics experts will be assessing the safety and efficacy of the interventions during the trial and perform ongoing monitoring of overall study conduct. The DMC's role and responsibilities and the scope of study oversight are detailed in the DMC Charter, which defines the DMC membership, meeting logistics, and meeting frequency.

After initiation of the study, the DMC will meet regularly (i.e., after enrollment of every 15 subjects through Stage 1 and once every three months from the start of Stage 2 until the last study subject has been enrolled, and then once every six months after completing Stage 2 enrollment through Week 264. In accordance with the DMC Charter, the DMC will provide recommendations for continuing or stopping the study based on their ongoing review of cumulative safety data, including reasons for screening failure, subject disposition, AEs, SAEs, device deficiencies, protocol deviations, and concomitant medications, as well as descriptive summaries of TJC28 and SJC28. At the end of Stage 1, the DMC will review the outcomes of a formal interim analysis (see Section 4.2). Closed Sessions will occur until the study is unblinded after data lock and primary analysis.

4.2 Interim Analysis

One formal interim analysis is planned at the end of Stage 1 when approximately 60 randomized subjects have reached their Week 12 endpoints. The purpose of this interim analysis is to check for safety risks and a lack of efficacy prior to commencing enrollment for Stage 2. No early success stopping may possibly occur. Therefore, there is no alpha-spending as there is no possibility for early claim. As these data contribute to the overall device experience for the safety review, and no early success stopping is permissible, no Type I error inflation occurs with such interims.

4.2.1 Stopping rule

The DMC and FDA will review the 12-week unblinded data from Stage 1, including demographics, efficacy, safety, enrollment rates, and device implantation rates, and determine whether the following stopping rule is met:

- The observed difference between treatment and control in the proportion of subjects achieving the ACR20 response at Week 12 from baseline on the day of informed consent is less than 10%.

This stopping rule in 60 subjects balances the need to stop a trial with a projected low probability of success with a need to avoid prematurely stopping a potentially successful trial after Stage 1, given the decision is based on a dichotomous endpoint in a relatively small number of subjects.

For illustrative purposes, the table below provides stopping probabilities for 60 randomized subjects and their effect on power in 250 randomized subjects, using an estimated ACR20 response rate of 30% in the control group and a range of 35-60% in the treatment group (**Table 2**). The proposed rule has a 50% probability of stopping a study having < 30% power to meet the primary efficacy objective in 250 subjects. Type 1 error is maintained at 2.5% even without the futility stop. The last column in the table shows power if enrollment ends at 240 subjects. Again, the power decreases by < 1% in all scenarios.

Table 2: True Probability of Stopping after Stage 1 and Power of Study Success Based on Pooled Data

Control	Treatment	Probability of Stopping		Power N = 250 (Stage 1 + 2)	Power N = 240 (Stage 1 + 2)
		N = 60 (Stage 1)			
30%	60%	0.040		0.959	0.959
30%	55%	0.089		0.900	0.898
30%	50%	0.173		0.773	0.770
30%	45%	0.293		0.555	0.549
30%	40%	0.444		0.291	0.282
30%	35%	0.608		0.096	0.093
30%	30%	0.760		0.017	0.017

Operating characteristics calculated by simulating 1,000,000 trials per scenario using chi-square test.

4.2.2 Communication plan

The Stage 1 efficacy and safety data for all 60 enrolled and randomized subjects will be exported from the database and directly delivered to an independent, non-voting, biostatistician who will analyze the data and report to the DMC without any involvement from the sponsor and study biostatisticians (**Table 3**). The independent biostatistician will analyze the data by randomization group, create an interim report and submit the report with the datasets, programs and program outputs to the DMC. The interim report will be reviewed by the DMC in a Closed Session. The DMC Chairperson will convey whether or not the stopping rule is triggered to the Chief Executive Officer (CEO) of SetPoint Medical.

If the stopping rule is triggered, the CEO or designee will notify the FDA about the DMC's decision and the study will be terminated. The study will be unblinded, and all Stage 1 data analyzed. The sponsor will submit to the FDA a report with the DMC's decision together with the datasets, programs and program outputs as well as any proposals for further clinical research.

If the stopping rule is not triggered, the sponsor will initiate an IDE Supplement to the FDA to request commencement of Stage 2 enrollment, and will provide the name and contact information

of the statistician from whom the FDA will request the Interim Report containing unblinded data. The unblinded data will be provided directly to the FDA upon request, maintaining blinding of the sponsor. The study will advance to Stage 2 only after receiving approval from the FDA.

The DMC Chairperson may also convey to the CEO the point estimates for ACR20 response rate in the treatment and control groups, if requested by the Board of Directors or potential key investors as a contingency for financing of Stage 2. The request and response will be documented and not shared with anyone directly or indirectly involved in the management of the study. The access to and communication of the interim findings will be tightly controlled to mitigate the introduction of operational bias and documented in reports submitted by the CEO to the DMC Chairperson following the communication procedures detailed in the DMC Charter.

Table 3: Interim Data Access Matrix

Department/Role	Blinded	Unblinded	Note
CEO	B	--	Receiving DMC's recommendations and decision as yes or no on the Stage 1 stopping rule and point estimates if requested by the board or investors as a contingency for financing Stage 2
Clinical Operations ¹	B	--	Not having access to randomization assignments or DMC Closed Session reports to preserve blinding of everyone involved directly or indirectly in the study conduct until locking the study dataset for the primary efficacy analysis at Week 12
Clinical Data Management	B	--	Consultants to sponsor responsible for managing EDC and IRT, generating blinded data exports and not having access to randomization assignments until locking the study dataset for the primary efficacy analysis at Week 12
Study Biostatisticians	B	--	Consultants to sponsor responsible for programming but not having access to randomization assignments until locking the study dataset for the primary efficacy analysis at Week 12
Independent Biostatistician	--	U	Non-voting statistician reporting to DMC responsible for receiving blinded data exports, accessing randomization assignments, conducting unblinded analyses and preparing outputs for review during DMC closed sessions
DMC	--	U	DMC chairperson, biostatistician, and clinicians participating in closed meetings

Abbreviations: B, blinded; CMO, Chief Medical Officer; CRA, clinical research associates; DMC, data monitoring committee; EDC, electronic data capture; IRT, Interactive response technology; U, unblinded;

¹Clinical operations includes, but is not limited to, Chief Medical Officer, Vice President of Clinical Affairs, Managers of Clinical Affairs/Operations, Clinical Research Associates, Field Clinical Engineers

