17.1 Randomization

After completing Day 0 assessments, all enrolled subjects will be assigned in a 1:1 ratio to either the treatment or the control group. The randomization will be stratified to help ensure balanced distribution between treatment groups of subjects with: inadequate response or loss of response to JAKi; inadequate response or loss of response to ≥ 4 biological DMARDs (bDMARDs) with ≥ 2 mechanisms of action; and those with < 4 TCJ28 or < 4 SJC28 at Day 0. The randomization scheme will be generated by the study biostatisticians and implemented centrally through an IRT.

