Conversely, with this stopping rule, there is 17% probability of stopping a study having 77% power to detect a 20% difference, highlighting the need for a balanced approach on stopping rules based on a dichotomous endpoint with just 60 subjects.

Based on their review, the DMC will convey their decision to terminate the study if the stopping rule is triggered or continue to Stage 2 as planned to the Chief Executive Officer (CEO) of SetPoint Medical or a designee. In the event the stopping rule is triggered, the CEO or designee will notify the FDA about the DMC's decision and the study will be terminated. The study will be unblinded, and all Stage 1 data analyzed. The sponsor will submit to the FDA a report with the DMC's decision together with the datasets, programs and program outputs as well as any proposals for further clinical research. If the stopping rule is not triggered, the sponsor will initiate an IDE Supplement to the FDA to request initiation of Stage 2 enrollment, and providing the name and contact information of the independent statistician from whom the FDA will request the Interim Report containing unblinded data. The unblinded data will be provided directly to the FDA upon request, maintaining blinding of the sponsor. The study will advance to Stage 2 only after receiving approval from the FDA.

The DMC will continuously monitor subject safety throughout Stages 1 and 2 and can stop the study anytime if serious safety concerns arise, as detailed in the DMC Charter.

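### The access rules conflict: the CEO is classed as blinded but may receive Stage 1 ACR20 rates by arm, and the study biostatisticians are classed as blinded but generate the randomization scheme

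*SAP*

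**What the plan says.** **CEO.** Protocol 17.3 has the DMC tell the CEO or a designee whether the study stops or continues. If it continues, "The unblinded data will be provided directly to the FDA upon request, maintaining blinding of the sponsor". SAP 4.2.2 repeats that sentence. The next SAP paragraph adds that "The DMC Chairperson may also convey to the CEO the point estimates for ACR20 response rate in the treatment and control groups", where the Board or a prospective investor asks for them before funding Stage 2. A safeguard follows: "The request and response will be documented and not shared with anyone directly or indirectly involved in the management of the study". The section also says access will be tightly controlled and reported under the DMC Charter. SAP Table 3 marks the CEO B, with a dash under Unblinded, while the note in that row reads "Receiving DMC's recommendations and decision as yes or no on the Stage 1 stopping rule and point estimates". Protocol Table 6 lists all sponsor representatives except the unblinded technicians as blinded. Table 1 of the long-term SAP gives the CEO only DMC recommendations.

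**Study biostatisticians.** Protocol 17.1 states: "The randomization scheme will be generated by the study biostatisticians and implemented centrally through an IRT". SAP 5.5 says the same. SAP Table 3 marks this group B and describes them as "responsible for programming but not having access to randomization assignments until locking the study dataset for the primary efficacy analysis at Week 12". Protocol Table 6 also lists them as blinded. The same Protocol table classes as not blinded the technicians who can open the database holding the scheme, and Protocol 11.5.2 gives those technicians sole access to a subject's assignment.

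**The concern.** A person who may hold the primary-endpoint rate in each arm is not blinded to the interim comparison, whatever letter the table gives. Stage 1 is pooled into the primary test. The plan's argument that Type I error is unaffected rests on there being no early success stop. That argument covers the stopping rule. It does not cover choices made about Stage 2 by someone who knows the Stage 1 effect, and the SAP itself names operational bias as the risk to be mitigated.

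The biostatistician rows raise a related question. Those who program the analysis are said both to make the scheme and to have no access to assignments. Both can be true only if someone else holds the final list, and the documents do not say who.

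At stake is whether the sponsor can show, from its own documents, that revisions, the decision to stop between 240 and 250 subjects, and the sponsor's deviation review (SAP 9.2) were made without knowledge of the effect.

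**Working it through.** **1. The plan's own figures.** Inputs from Protocol Tables 4-5 and SAP Tables 1-2: control rate 30%, 60 subjects in Stage 1, 250 in total, one-sided alpha 0.025, stop if the observed difference is below 10%. I assume 30 per arm in Stage 1 and 125 per arm in total, from 1:1 allocation. The trial continues if treatment responders minus control responders is at least 3. The final test is

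z = [(t − c)/125] / √[p̄(1 − p̄)·2/125] > 1.96, with p̄ = (t + c)/250.

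Exact binomial enumeration gives:

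| True rates (control, treatment) | Stopping: plan | Stopping: exact | Power: plan | Power: exact |
|---|---|---|---|---|
| 30%, 60% | 0.040 | 0.0403 | 0.959 | 0.9586 |
| 30%, 50% | 0.173 | 0.1727 | 0.773 | 0.7736 |
| 30%, 30% | 0.760 | 0.7596 | 0.017 | 0.0172 |

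The figures reproduce. No design figure changes under this point.

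**2. Weight of Stage 1.** 60/250 = 24%; 60/240 = 25%.

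**3. What the rates add to the bare decision.** The decision to continue tells the CEO only that the difference was at least 10 points. The rates allow conditional power to be computed. Assume 9/30 control responders in Stage 1 and 95 per arm in Stage 2, with the same final test:

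| Stage 1 treatment responders | Observed difference | Conditional power, true rates 45% vs 30% | Conditional power at the observed trend |
|---|---|---|---|
| 12/30 | 10 points | 0.64 | 0.37 |
| 18/30 | 30 points | 0.89 | above 0.99 |

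These values are illustrative. They show that the estimates are informative. They do not measure bias.

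**4. CEO rules side by side.**

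| Place | What the CEO may have |
|---|---|
| Protocol 17.3 | Stop-or-continue decision |
| Protocol Table 6 | Blinded, as a sponsor representative |
| SAP 4.2.2, FDA paragraph | Sponsor blind maintained |
| SAP 4.2.2, next paragraph | ACR20 estimates by arm, on request |
| SAP Table 3 | B, with a note granting the estimates |
| Long-term SAP Table 1 | DMC recommendations only |

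The SAP permission contradicts the label in its own row and goes beyond the Protocol. The safeguard controls who else may learn the estimates. Nothing in 4.2.2 or Table 3 bars a CEO who has them from taking part in Protocol or SAP revisions or in deciding when enrolment ends.

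**5. Biostatistician rules side by side.** Protocol 17.1 and SAP 5.5 make this group the generator. SAP Table 3 and Protocol Table 6 make it blinded. Protocol Table 6 treats access to the scheme as incompatible with blinding when technicians have it. No step is described that separates generating the scheme from holding the final list or seed.

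**The case against.** The strongest reply is that the disclosure is narrow and openly stated. It is optional, needs a Board or investor request, covers two aggregate rates, must be documented and may not reach anyone managing the study. Protocol 18.3 frames the blind as one to randomized assignment, and two arm-level rates reveal no subject's assignment. The DMC Charter, not among the documents here, may add controls. FDA, which can obtain the unblinded report, must approve Stage 2. All of this stands, and it keeps the point at the level of inconsistent rules. It does not reconcile a B label with a note that grants interim efficacy by arm, and it supplies no recusal.

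On the biostatisticians, generating a scheme that is run centrally through the IRT does not prove possession of the live list. That stands too; what is missing is a stated firewall.

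Three stronger readings are tempting, and the documents support none of them.

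- A reader might infer that the biostatisticians hold the list. The text says only that they generate a scheme, and it denies them access to assignments.
- A reader might infer that pooling without alpha adjustment was premised on nobody knowing the effect. The stated reason in Protocol 17.3 and SAP 4.2 is the absence of an early success stop.
- A reader might note that several amendments came after Stage 1 and infer that they were data-driven. The dates show neither that estimates were released nor that the CEO shaped any change, and the 240 floor slightly lowers power (at most 0.762 to 0.750 in SAP Table 1).

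**Conclusion.** The point holds as a conflict in the access rules. A role labelled blinded may receive Stage 1 ACR20 by arm, the Protocol does not grant this, and no recusal is stated. A second role labelled blinded generates the randomization scheme, with no stated custody of the final list. A reader might conclude that the sponsor's blind failed. The documents show no breach, no individual unblinding and no change in Type I error.

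The exposure is operational bias around 24-25% of the primary data. The conditional powers of 0.64 and 0.89 depend on the assumed 9/30 control responders, 30 per arm in Stage 1, 95 per arm in Stage 2 and true rates of 45% and 30%. They show only how informative the estimates would be. Whether estimates were ever requested or released cannot be told from the documents. The correction should be made, since it is cheap and lets the sponsor demonstrate independence.

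**What to change.** 1. **CEO.** If the permission was never used, remove it from SAP 4.2.2 and the Table 3 note. If it was used, keep the record. Mark the CEO as unblinded to aggregate interim results in SAP Table 3 and Protocol Table 6, align Protocol 17.3, and state whether and when estimates were released. State also that the CEO takes no part in Protocol or SAP revisions, the decision to end enrolment, or deviation review.
2. **Randomization list.** In Protocol 17.1 and SAP 5.5, state that the final list and seed are generated and held by a statistician independent of the study biostatisticians, for example the Independent Biostatistician, who is already unblinded. If the study biostatisticians did hold the final list, mark them unblinded and have someone without the list confirm the SAP Revision C changes and the deviation review.
3. **Supportive analysis.** Add ACR20 for Stage 1 and Stage 2 separately, with a Breslow-Day test, which the SAP already uses for subgroups. SAP 8.3.4 and 8.3.5 list no analysis by stage.

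The cost is wording in two tables and a few sections, a dated disclosure statement and one extra table. The Stage 2-only estimate is less precise: at equal response rates its standard error is √(125/95) = 1.15 times that of the pooled estimate, so it should be supportive only.
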